#### **4.1.3. Subgroup Analyses**

The homogeneity of treatment effect on the occurrence of the primary endpoint across subgroups will be examined (at a 2-sided significance level of 0.05) via a test for the treatment by subgroup interaction by adding this term and the subgroup as covariates (treated as class variables) to the primary efficacy analysis (Section 4.1.2) model. Subgroup analysis will be conducted when the total number of events is greater than 10 for two treatment groups (all canagliflozin group and placebo) and at least 1 event in both groups. Factors exhibiting interactions at a significance level of  $p < 0.05$  will be identified as suggesting treatment effect heterogeneity, recognizing the multiplicity in testing multiple subgroups such that one or more p-values  $< 0.05$  may be expected to be observed by chance alone.

If a significant interaction is observed, the Gail-Simon test will be used to further examine the nature of the interaction (qualitative or quantitative).

The hazard ratio of canagliflozin (all canagliflozin group) compared to placebo and its 95% confidence interval will be estimated for each of the following subgroups:

- Age group:  $<65, \geq 65$  years old;
- Sex: Male, Female;

- Race: White, Black or African American, Asian, Other;
- Region: Central/South America, Europe, North America, Rest of the World;
- Baseline BMI categories ( $<30$ ,  $\geq 30$  kg/m^2);
- Baseline composite blood pressure categories ([SBP $<140$  or DBP $<90$  mmHg] vs. [SBP  $\geq 140$  and DBP  $\geq 90$  mmHg]);
- Baseline eGFR categories (30 to  $<60$ , 60 to  $<90$ ,  $\geq 90$  mL/min/1.73m^2);
- Baseline HbA1c  $\geq 8\%$ : Yes/No;
- Baseline albuminuria: Normoalbuminuria, Microalbuminuria;
- Duration of diabetes  $\geq 10$  years: Yes/No;
- History of CV disease: Yes/No;
- Baseline use of Renin angiotensin aldosterone system (RAAS) inhibitor: Yes/No.

#### **4.1.4. Supportive Analyses**

If not otherwise specified, the supportive analyses will use the same analysis set as in the primary efficacy analysis.

##### **4.1.4.1. On-Treatment Analysis**

For On-Treatment analysis, endpoint events that occur within the data period (see [Table 1](#)) will be eligible events; otherwise subjects will be censored at the earliest of the last ACR measurement date, last study drug dose date + 30 days, or GTED.

The Cox model for primary analysis (as described in [Section 4.1.2](#)) will be repeated using the On-Treatment analysis set.

##### **4.1.4.2. Additional Supportive Analyses**

Several Cox models analogous to the primary efficacy analysis model will also be performed for exploratory purposes:

- The first Cox proportional hazards model involves the use of confirmed progression, plus the unconfirmed progression from the last ACR values;
- Secondly, there will be an analysis that only excludes subjects with baseline nephrotic range macroalbuminuria (ie, ACR  $> 3000$  mg/g). This analysis will evaluate time to first occurrence of  $\geq 1$  step progression in the following categories (ie, baseline normoalbuminuria, baseline microalbuminuria, baseline non-nephrotic range macroalbuminuria).

Additionally, the actual onset time of progression of albuminuria can be determined to occur within an interval from a sequence of examination times (ie, data are interval censored). The accelerated failure time (AFT) model with log normal error structure will be implemented considering interval censoring excluding subjects with baseline macroalbuminuria. The dependent variable in the AFT model is the logarithm of time to progression of albuminuria,

expressed as time intervals. The model will include treatment group and baseline albuminuria status as the explanatory variables.

The cumulative progression rate derived from Kaplan-Meier estimate will be displayed graphically to evaluate the timing of progression and the consistency of the treatment effect over time.

#### **4.1.4.3. Assessment of Missing Data**

The potential impact of missing data in the interpretation of the primary efficacy analysis will be explored. The primary efficacy endpoint, progression of albuminuria was derived from urinary albumin/creatinine ratio (ACR) laboratory measurements which were generally collected biannually while subjects were on treatment (ie on treatment period) up to the global trial end date (GTED). For subjects who discontinue from treatment early before the development of progression of albuminuria, unobserved data of post-baseline ACR measurements at each scheduled visit up to the GTED will be considered missing and will be imputed. The multiple imputation procedure will apply to ACR data and the time to ACR progression data will then be generated based on the imputed data at the schedule visits.

#### **Data for model development**

Due to the staggered enrollment of the study, for those randomized at a later stage of the enrollment period, pseudo visits up to the max possible visit week prior to GTED, i.e. week 130, will be created according to the protocol schedule. In addition, multiple data points at each visit, e.g. confirmatory samples, will be aggregated using geometric mean according to the variability of ACR data. There is small proportion of subjects (less than 2.5%) with unscheduled visits which will be combined with the closest scheduled visit using the same approach.

#### **Imputation model**

Assuming that after treatment discontinuation, subjects discontinued from the canagliflozin arm will exhibit a response similar to subjects in the placebo arm, the imputation model will be fit using the non-missing data in the placebo group and adjusted for covariates that may be related to the missing data mechanism and the risk of progression based on clinical judgment. The potential covariates include:

- Baseline ACR (continuous);
- Baseline eGFR categories (30 to <60, 60 to <90,  $\geq 90$  mL/min/1.73m^2);
- Baseline blood pressure (SBP<140, DBP<90 mmHg): Yes/No;
- Baseline HbA1c  $\geq 8\%$ : Yes/No;
- Age group: <65,  $\geq 65$  years old;
- Race: White, Other;
- Sex: Male, Female;

In case of convergence issues, the covariates will be removed from the model in the descending order of the list (ie, starting from the bottom of the list).

Due to the highly skewed data of ACR, both baseline and post baseline ACR in the imputation model will be log transformed.

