Increase dose if subject requires additional glycemic control (see Section 3.1)						X	X		X		
Procedures											
Vital signs, weight, foot examination ^f	X	X				X	X		X	(ask about foot problems and provide foot care guidance)	X
Serum chemistry panel ^g	X	X				X	X		X		X
Hematology ^g		X							Week 52, 104 and 156		X
Fasting serum lipid profile ^g		X					X		Week 52, 104 and 156		X
HbA _{1c}	X	X				X	X		X		X
Duplicate first morning void urines for urine albumin/creatinine (provide collection containers at previous visit) ^{g, h}		X					X		Weeks 52, 78, 104 and 156		X
Urinalysis ^g		X									

Procedures and Evaluations	Pre-treatment		Double-blind treatment						
	Screening ^a	Baseline	Phone/email contact at Week 6	Week 13	Week 26	Phone/email contact at Week 39	Week 52 and thereafter unless otherwise indicated	Phone/email contact midway between 26-week visits until last on-treatment visit	Last on-treatment visit (or after early discontinuation of treatment) ^b
Time point	Week -2	Day 1							
Urine pregnancy test ¹		X							
Dispense glucose testing supplies (optional per country/region)		X		X	X		X		
Ongoing Review									
Concomitant therapy (drug classes of interest) ^j			X	X	X	X	X	X	X
Serious adverse events, and AEs causing discontinuation; vital status; AEs of interest ¹		X	X	X	X	X	X	X	X
CV events		X	X	X	X	X	X	X	X

For footnotes, see below

TIME AND EVENTS SCHEDULE: POSTTREATMENT

Posttreatment

Procedures and Evaluations		Posttreatment Follow-up		
		All Subjects	Subjects Who Withdraw Prior to End of Study	Subjects Who Withdraw Prior to End of Study
Time point		Final visit 30 days after last on-treatment visit (or after early discontinuation of treatment; preferably 30 days after last dose of study drug) ^e	Visit every 26 weeks after last dose until notification of global trial end date (GTED) ^b	Phone/email contact midway between 26 week visits until notification of the GTED ^{b,n}
Procedures				
Vital signs, weight, foot examination ^f			X	X (ask about foot problems and provide foot care guidance)
Serum chemistry panel ^g		X		
Hematology ^g				
Fasting serum lipid profile ^g				
HbA _{1c}				
Duplicate first morning void urines for urine albumin/creatinine (provide collection containers at previous visit) ^{g,i,h}				
Urine pregnancy test ⁱ				
Dispense glucose testing supplies (optional per country/region)				
Ongoing Review				
Concomitant AHA therapy ^j				X

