4.3. Exclusion Criteria

Potential subjects who meet any of the following criteria will be excluded from participating in the study:

Diabetes-Related/Metabolic

- History of diabetic ketoacidosis, T1DM, pancreas or beta-cell transplantation, or diabetes secondary to pancreatitis or pancreatectomy
- History of one or more severe hypoglycemic episodes within 6 months before screening
Note: a severe hypoglycemic episode is defined as an event that requires the help of another person.
- History of hereditary glucose-galactose malabsorption or primary renal glucosuria
- Ongoing, inadequately controlled thyroid disorder
Note: subjects on thyroid hormone replacement therapy must be on a stable dose for at least 6 weeks before Day 1.

Renal/Cardiovascular

- Renal disease that required treatment with immunosuppressive therapy or a history of chronic dialysis or renal transplant. Note: subjects with a history of treated childhood renal disease, without sequelae, may participate.
- Myocardial infarction, unstable angina, revascularization procedure, or cerebrovascular accident within 3 months before screening, or a planned revascularization procedure, or history of New York Heart Association (NYHA) Class IV cardiac disease ([The Criteria Committee of the New York Heart Association](#)).
- Known ECG findings within 3 months before screening that would require urgent diagnostic evaluation or intervention (eg, new clinically important arrhythmia or conduction disturbance)

Gastrointestinal

- Known history of hepatitis B surface antigen or hepatitis C antibody positive (unless known to be associated with documented persistently stable/normal range aspartate aminotransferase [AST] and alanine aminotransferase [ALT] levels), or other clinically active liver disease
- Any history of or planned bariatric surgery

Laboratory

- eGFR <30 mL/min/1.73m² at screening visit
- ALT levels >2.0 times the upper limit of normal (ULN) or total bilirubin >1.5 times the ULN, unless in the opinion of the investigator and as agreed upon by the sponsor's medical officer, the findings are consistent with Gilbert's disease

Other conditions

- History of malignancy within 5 years before screening (exceptions: squamous and basal cell carcinomas of the skin and carcinoma of the cervix in situ, or a malignancy that in the opinion of the investigator, with concurrence with the sponsor's medical monitor, is considered cured with minimal risk of recurrence)

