- History of human immunodeficiency virus (HIV) antibody positive
- Subject has a current clinically important hematological disorder (eg, symptomatic anemia, proliferative bone marrow disorder, thrombocytopenia)
- Investigator's assessment that the subject's life expectancy is less than 1 year, or any condition that in the opinion of the investigator would make participation not in the best interest of the subject, or could prevent, limit, or confound the protocol-specified safety or efficacy assessments
- Major surgery (ie, requiring general anesthesia) within 3 months of the screening visit or any surgery planned during the subject's expected participation in the study (except minor surgery, ie, outpatient surgery under local anesthesia)
- Any condition that, in the opinion of the investigator, would compromise the well-being of the subject or prevent the subject from meeting or performing study requirements

Medications/Therapies

- Current or prior use of an SGLT2 inhibitor.
- Prior or current participation in another canagliflozin study.
- Known allergies, hypersensitivity, or intolerance to canagliflozin or its excipients (refer to Section 14.1, Physical Description of Study Drug[s])
- Current use of a corticosteroid medication or immunosuppressive agent, or likely to require treatment with a corticosteroid medication (for longer than 2 weeks in duration) or an immunosuppressive agent. **Note:** subjects using inhaled, intranasal, intra-articular, or topical corticosteroids, or corticosteroids in therapeutic replacement doses may participate
- Received an active investigational drug (including vaccines) or used an investigational medical device within 3 months before Day 1/baseline

General

- History of drug or alcohol abuse within 3 years before screening
- Pregnant or breast-feeding or planning to become pregnant or breast-feed during the study
- Employees of the investigator or study center, with direct involvement in the proposed study or other studies under the direction of that investigator or study center, as well as family members of the employees or the investigator

Note: Investigators should assure that all study enrollment criteria have been met and determine that the subject has not had any interval change in clinical status since screening. Before randomization, subjects whose status changes after screening, such that they now meet an exclusion criterion, should be excluded from participation.

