Attachment 1: Clinical Laboratory Tests

Blood samples for serum chemistry and hematology, and a baseline random urine sample for urinalysis will be collected. The investigator must review the laboratory report, document this review, and record any clinically relevant changes occurring during the study in the adverse event section of the eCRF and take appropriate action (eg, repeating abnormal laboratory result or further evaluation as considered clinically appropriate). The following tests will be performed by the central laboratory.

- Hematology Panel
 - hemoglobin
 - hematocrit
 - white blood cell (WBC) count with differential
 - platelet count
 - red blood cell (RBC) count
- Serum Chemistry Panel
 - sodium
 - potassium
 - chloride
 - bicarbonate
 - blood urea nitrogen (BUN)
 - creatinine
 - aspartate aminotransferase (AST)
 - alanine aminotransferase (ALT)
 - gamma-glutamyltransferase (GGT)
 - total bilirubin
 - alkaline phosphatase
 - creatine phosphokinase (CPK)
 - lactic acid dehydrogenase (LDH)
 - uric acid
 - calcium
 - phosphate
 - albumin
 - total protein
 - magnesium
- Fasting serum lipid profile (triglycerides, LDL-C, HDL-C, total cholesterol).
- HbA_{1c}
- Urinalysis (dipstick analysis; from spot urine collection in the clinic on Day 1; performed at central laboratory; microscopic analysis is not required)*
 - specific gravity
 - pH
 - protein
 - blood
 - ketones
 - bilirubin/urobilinogen
 - nitrite
 - leukocyte esterase

*Urine glucose will not be measured by the central laboratory

Central laboratory will report the eGFR according to the Modification of Diet in Renal Disease Study (MDRD) equation ([Levey 2006](#)) at study visits when serum creatinine is measured. The 4-variable MDRD eGFR includes serum creatinine, age, race, and sex according to the equation below:

For creatinine in mg/dL:

$$\text{eGFR (mL/min/1.73 m}^2\text{)} = 175 \times (\text{serum creatinine})^{-1.154} \times (\text{age})^{-0.203} \\ \times (0.742 \text{ if female}) \times (1.21 \text{ if black})$$

For creatinine in μmol/L:

$$\text{eGFR (mL/min/1.73 m}^2\text{)} = 175 \times (\text{serum creatinine} \times 0.0113)^{-1.154} \times (\text{age})^{-0.203} \\ \times (0.742 \text{ if female}) \times (1.21 \text{ if black})$$

INVESTIGATOR AGREEMENT

JNJ-28431754: Canagliflozin

Clinical Protocol 28431754DIA4003 – Amendment INT-5

INVESTIGATOR AGREEMENT

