#### 3.2. Baseline Disease Characteristics

Descriptive statistics (N, mean, SD, median, and range) will be provided by treatment group and overall for the following baseline continuous variables: duration of diabetes (in years), baseline eGFR, baseline ACR, systolic blood pressure (SBP), weight, body mass index (BMI), HbA1c, LDL-C, HDL-C, triglycerides, total cholesterol and LDL-C/HDL-C.

Additionally, the number and percentage of subjects will be summarized by treatment group and overall for the following:

- Baseline BMI categories (<30, ≥30 kg/m^2);
- Currently daily cigarette smoker: Yes/No;
- Baseline HbA1c ≥ 8%: Yes/No;
- Duration of T2DM ≥ 10 years: Yes/No;
- Baseline systolic blood pressure categories (≤140, >140 mmHg);
- Baseline LDL-C categories (≤70, >70 mg/dL);
- Baseline HDL-C categories (<39, ≥39 mg/dL);
- Baseline eGFR categories (<30, 30 to <60, 60 to <90, ≥90 mL/min/1.73m^2);
- Baseline albuminuria category:
  - Normoalbuminuria (0 ≤ ACR <30 mg/g); Microalbuminuria (ACR ≥30 mg/g and ≤300 mg/g); Macroalbuminuria (ACR >300 mg/g: ACR >300 mg/g and ≤3000 mg/g, ACR > 3000 mg/g).
- History of hypertension: Yes/No ;
- History of CV disease: Yes/No;

- History of coronary artery disease: Yes/No;
- History of cerebrovascular disease: Yes/No;
- History of peripheral vascular disease: Yes/No;
- History of heart failure: Yes/No;
- Microvascular diabetes complications (Any, 1, 2 or 3 of retinopathy, neuropathy [diabetic or automatic neuropathy] and nephropathy)
- History of fracture: Yes/No;

The number and percentage of subjects with a history of medical conditions by system organ class and preferred term (based upon the general medical history eCRF) will be summarized by treatment group and overall.

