#### **4.4.2. Analysis Methods**

##### **4.4.2.1. Renal Endpoints**

###### **4.4.2.1.1. Composite Endpoints**

The components of the renal composite endpoints, such as requirement for renal replacement therapy and doubling of serum creatinine, identified by the investigator or the sponsor for meeting the criteria pre-specified in the charter will be sent to the independent EAC.

The time to the first occurrence of each of the renal composite endpoints (see Section 4.4.1) will be analyzed in the ITT analysis set using a Cox proportional hazards model with treatment and baseline eGFR ( $< 60$ ,  $\geq 60$  mL/min/1.73m^2) as the explanatory variables. The hazard ratio of canagliflozin compared to placebo and its 95% confidence interval will be estimated from the model.

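### The SAP's eGFR subgroup and imputation categories start at 30, but baseline eGFR can fall below 30, so a few subjects have no category in those analyses

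*SAP*

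**What the plan says.** Protocol 4.3 sets the renal entry limit as "eGFR <30 mL/min/1.73m² at screening visit". It gives no separate limit for Day 1. A general note at the end of the same section says: "Before randomization, subjects whose status changes after screening, such that they now meet an exclusion criterion, should be excluded from participation".

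The Time and Events Schedule has the row "Serum chemistry panel ^g" marked at screening and again on Day 1. Protocol Attachment 1 has the central laboratory report eGFR "at study visits when serum creatinine is measured". Each subject should therefore have two pre-dose eGFR values.

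SAP 2.3.3 takes as baseline the pre-dose measurement nearest to or on Day 1. For serum creatinine it uses the mean of the last two pre-dose values. It does not say which of these rules governs baseline eGFR.

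The SAP then groups baseline eGFR in three ways:

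- SAP 3.2 (baseline table) has four levels: "Baseline eGFR categories (<30, 30 to <60, 60 to <90", then 90 and above.
- SAP 4.1.3 (primary-endpoint subgroups), SAP 4.1.4.3 (imputation model) and SAP 4.2.2.1 (composite of CV death or heart-failure hospitalization) have three levels: "Baseline eGFR categories (30 to <60, 60 to <90", then 90 and above. SAP 4.2.2.2 reuses the 4.2.2.1 subgroups for CV death.
- SAP 4.4.2.1.1 (renal composites) has two levels, split at 60: "using a Cox proportional hazards model with treatment and baseline eGFR".

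**The concern.** The three-level lists do not cover every value that baseline eGFR can take, and no rule places a subject below 30. SAP 4.1.3 enters each subgroup factor as a class variable with a treatment interaction. A subject with no level contributes to none of the eGFR subgroup hazard ratios and, under usual software defaults, is dropped from the interaction model. In the imputation, a regression that includes this covariate can neither learn from nor predict for a subject whose covariate is undefined, unless the programmer adds a rule.

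The subjects concerned have the lowest renal function in the trial, and the eGFR subgroup analysis is where a reader would look for them. The handling would also be settled in programming rather than in the plan.

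**Working it through.** **1. Can an eligible subject have baseline eGFR below 30?** There are two readings of SAP 2.3.3.

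- *Baseline eGFR is the Day 1 value.* Any subject at 30 or more at screening and below 30 on Day 1 qualifies.
- *Baseline eGFR is calculated from the averaged creatinine.* In the MDRD equation of Attachment 1, eGFR is proportional to creatinine^(−1.154), with age, sex and race terms that cancel here. Creatinine is therefore proportional to eGFR^(−1/1.154), and

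  baseline eGFR = [ (E1^(−1/1.154) + E2^(−1/1.154)) / 2 ]^(−1.154),

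  where E1 is the screening value and E2 the Day 1 value.
  - E1 = 31, E2 = 28: (0.05101 + 0.05571)/2 = 0.05336, which gives 29.4. No category.
  - E1 = 32, E2 = 29: gives 30.4. Categorized.
  - For screening values of 30, 32, 35 and 40, the Day 1 value must be below 30.0, 28.2, 26.2 and 23.8 for the baseline to fall below 30.

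The gap exists under both readings and is narrower under averaging.

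**2. Which analyses use the three-level variable?**

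| Analysis | eGFR term | Covers below 30? |
|---|---|---|
| Baseline table (SAP 3.2) | four levels | yes |
| Primary Cox model (4.1.2) | none | not needed |
| Primary-endpoint eGFR subgroup (4.1.3) | three levels | no |
| ACR imputation model (4.1.4.3) | three levels, listed as a potential covariate | no |
| Cox model after imputation (4.1.4.3) | none; same model as 4.1.2 | not needed |
| Secondary Cox models (4.2.2.1, 4.2.2.2) | none; stratified by history of CV disease | not needed |
| Secondary eGFR subgroups (4.2.2.1, 4.2.2.2) | three levels | no |
| Renal composites (4.4.2.1.1) | split at 60 | yes |

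**3. How many subjects?** The documents give no eGFR distribution, so this step rests on assumptions: true eGFR normal with mean 70 to 78 and SD 18 to 22, and two independent lognormal measurements with a within-person CV of 6% to 10%. Among simulated subjects with a screening value of 30 or more, applied to the 5,812 recruited (SAP 1.1), the proportion with baseline below 30 is:

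- Day 1 reading: 0.07% to 0.64%, about 4 to 37 subjects.
- Averaged-creatinine reading: 0.03% to 0.28%, about 2 to 17 subjects.

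The low end is mean 78, SD 18, CV 6%. The high end is mean 70, SD 22, CV 10%. The primary-endpoint analyses would contain fewer, because SAP 4.1 excludes baseline macroalbuminuria and subjects without baseline or post-baseline ACR.

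**4. Does any stated figure change?** Protocol 11.2 gives 693 events, a 22% reduction (hazard ratio 0.78) and 90.5% power at two-sided 0.05. Check: (√693 / 2) × |ln 0.78| − 1.960 = 13.162 × 0.2485 − 1.960 = 1.310, and Φ(1.310) = 0.905. The figure reproduces. It belongs to a model with no eGFR term, so the category gap does not affect it.

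**The case against.** Several points limit the concern.

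- *The re-check before randomization.* Investigators are told to exclude subjects who come to meet an exclusion criterion after screening. This reduces the number but does not close the gap. The eGFR criterion is tied to the screening visit, the Day 1 sample is taken on the day of randomization and first dose, and its result comes from a central laboratory. SAP 3.2 still lists a level below 30.
- *Averaged creatinine.* If baseline eGFR follows the averaged creatinine, a Day 1 value below 30 does not by itself leave a subject uncategorized. This stands and lowers the count by more than half, but not to zero.
- *The imputation covariates are only potential ones.* This stands as a reason to say that the imputation may be affected rather than will be. However, covariates are dropped only for convergence problems and from the bottom of the list, and eGFR is second from the top.
- *A separate stratum below 30 would be too sparse to report.* SAP 4.1.3 requires more than 10 events in a subgroup. This supports folding these subjects into a category below 60, not leaving them without one.

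A reader might infer that these subjects also leave the Cox model re-run after imputation, so that the sensitivity analysis changes population as well as missing-data assumption. The documents do not support that. The re-run model is the primary one, with treatment and baseline albuminuria status only, and nothing in SAP 4.1.4.3 removes a subject for lacking an eGFR category. Subjects who complete treatment or progress keep their observed data. At most, a few early discontinuers might go without imputed values, and a few placebo subjects might not inform the imputation fit.

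**Conclusion.** The gap is real and internal to the SAP: the baseline table provides for values below 30, and three later lists do not. Its reach is narrow. It affects the eGFR subgroup hazard ratios and interaction test for the primary endpoint and the two secondary endpoints and, possibly, the imputation of a few subjects in one sensitivity analysis. Subjects below 30 remain in every other subgroup, and no confirmatory result or stated power depends on the variable.

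The estimate of about 2 to 37 of 5,812 subjects across both readings rests wholly on the assumed distribution and on no systematic change in eGFR between screening and Day 1; a fall over the run-in would raise it. That such subjects are dropped is an inference from the class-variable specification, since the SAP is silent on their handling. The point is worth correcting because it costs almost nothing, not because it threatens a conclusion.

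**What to change.** In SAP 4.1.3, 4.1.4.3 and 4.2.2.1, change the lowest eGFR category from 30 to <60 to simply <60. SAP 4.2.2.2 follows by reference. This agrees with the split at 60 in SAP 4.4.2.1.1, keeps three levels and avoids a sparse cell. In the imputation model, continuous baseline eGFR would serve equally well.

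Add one sentence to SAP 2.3.3 stating whether baseline eGFR is calculated from the averaged creatinine or taken as the last pre-dose eGFR. The four-level baseline table in SAP 3.2 can stay, since it will show how many subjects are below 30.

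The cost is a small edit in three lists and one added sentence, best made before unblinding. No sample-size, event or power figure needs revision.
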